3.3.2 Inclusion criteria

1) Phase I Dose Escalation:

- a. Male or female patients ≥ 18 years of age with relapsed or refractory AML (defined as persisting AML after at least two induction cycles) and no anti-leukemia therapy within 2 weeks before first treatment with decitabine.
- b. Male or female patients ≥ 65 years of age with previously untreated AML ineligible for receiving standard intensive therapy based on documented medical reasons as defined in [Section 5.6.1](#).

Phase I Extension and Phase II:

Male or female patients ≥ 65 years of age with previously untreated AML ineligible for receiving standard intensive therapy based on documented medical reasons as defined in [Section 5.6.1](#).

- 2) Histologically or cytologically confirmed AML according to the WHO classification ([R09-2581](#)).
- 3) Patients must be eligible for treatment with decitabine.
- 4) Eastern co-operative oncology group (ECOG) performance score ≤ 2 at screening
- 5) Signed and dated written informed consent (including consent for biomarker and genetic testing; refer to [Section 8.1](#)) by the start date of the Screening Visit in accordance with GCP and local legislation.

Please note that prior therapy for MDS is allowed for all patients participating in Phase I and Phase II of this trial (with the exception of hypomethylating agents such as decitabine and azazitidine).

Prior treatment with hydroxyurea in order to reduce high WBC and treatment with hydroxyurea to control the WBC count during the first treatment cycle is allowed (refer to [Section 4.2.2.1](#)).

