4.1.3.1 Treatment in the Phase I Dose Escalation part of the trial

The daily dose of decitabine will not be escalated (or reduced); however, the decitabine treatment schedule (i.e. the number of consecutive days with decitabine administration in each cycle) will be individually customized based on response and toxicity as per [Table 4.1.3.1: 1](#).

Table 4.1.3.1: 1 Decitabine intensive treatment schedule

Cycle	Blasts in % at end of precedent cycle	Decitabine i.v. treatment duration
Cycle 1	n.a.	20 mg/m ² for 10 consecutive days (Days 1-10 of 28-day cycle)
Cycle 2-3	No blasts in peripheral blood and BM blasts < 5%	20 mg/m ² for 5 consecutive days (Days 1-5 of 28-day cycle)
	Blasts in peripheral blood ≥ 5% (no BM assessment required) or No blasts in peripheral blood and BM blasts ≥ 5%	20 mg/m ² for 10 consecutive days (Days 1-10 of 28-day cycle)
Cycles 4 and further, until 'progression or toxicity'	non-PD patients*	20 mg/m ² for 5 consecutive days (Days 1-5 of 28-day cycle)

*) Only non-PD patients (i.e. patients without disease progression or relapse) will continue treatment within the trial.

In case the initially planned treatment duration (as assigned prior to Day 1 of any new cycle) is not considered to be safe by the Investigator (e.g. due to myelotoxicity in precedent cycle), Day 4 and/or Day 5 may be omitted in the current and all subsequent cycles.

The Phase I Dose Escalation for BI 836858 will be guided by a Bayesian logistic regression model (BLRM) with overdose control.

The dose is planned to be escalated in cohorts at pre-specified provisional dose levels based on a maximum escalation of 100%. The provisional dose levels to be assigned to separate cohorts of patients are listed in [Table 4.1.3.1: 2](#). Dose levels above 40 mg will only be explored after safety data from monotherapy studies with BI 836858 have become available and if data from PK and pharmacodynamics analysis support further dose escalation. Intermediate or lower dose levels, depending on the number of DLTs observed in the study, and dose levels higher than 320 mg, as long as they fulfil the safety criteria, may be investigated if recommended by SMC and agreed upon between Investigator and Sponsor.

Table 4.1.3.1: 2 BI 836858 dose escalation scheme

Cohort	BI 836858 i.v. weekly^{a), b)} in 28-day cycles	Decitabine i.v. in 28-day cycles
Cohort 1	[REDACTED]	20 mg/m ²
Cohort 2	[REDACTED]	20 mg/m ²

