5.2 ASSESSMENT OF EFFICACY

5.2.1 Overall response assessment

Response to treatment will be evaluated based on bone marrow samples (aspirations and biopsies will be collected as described in the [Flow Chart](#)) according to the following criteria (based on diagnosis and management of AML in adults: recommendations from an international expert panel, on behalf of the European Leukemia Net ([R10-2947](#))

- Complete remission (CR)
Bone marrow (BM) blasts < 5%; absence of blasts with Auer rods; absence of extramedullary disease; absolute neutrophil count $> 1.0 \times 10^9/L$ [1,000/ μ L]; platelet count $> 100 \times 10^9/L$ [100,000/ μ L]; independence of red blood cells transfusions (no transfusion for 1 week prior to the assessment). No minimum duration of response is required.
- Complete remission with incomplete neutrophil or platelet recovery (CRi)
All CR criteria except for residual neutropenia ($< 1.0 \times 10^9/L$ [1,000/ μ L]) or thrombocytopenia ($< 100 \times 10^9/L$ [100,000/ μ L]).
- Partial remission (PR)
All haematologic criteria of CR; decrease of bone marrow blast percentage to 5% to 25%; and decrease of pre-treatment bone marrow (baseline) blast percentage by at least 50%. Bone marrow samples with <5% blasts and with presence of Auer rods also represent PR.
- Stable disease (SD)
Patient alive with no CR, CRi, PR or PD.
- Progressive disease (PD)
Progressive disease is defined as at least one of the criteria below:
 - 50% increase in BM blast count over baseline (AML diagnosis);
 - 50% increase in peripheral blast count over baseline that is considered clinically relevant by the Investigator;
 - evidence of new extramedullary disease;

Proprietary confidential information © 2019 Boehringer Ingelheim International GmbH or one or more of its affiliated companies

- clinically progressive disease based on the judgement of the Investigator (any attempt should be made to verify clinically diagnosed PD by a BM assessment).
- Relapse (recurrence)
In patients with previous CR or CRi: Bone marrow leukemic blasts $\geq 5\%$ or reappearance of blasts in the blood not attributable to any other cause (e.g. bone marrow regeneration), or development of extramedullary disease.
- Death in aplasia

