The following should also be recorded as an (S)AE in the eCRF and SAE form (if applicable):

- Worsening of the underlying disease or of other pre-existing conditions (for exemptions see below in paragraph “Exemptions to (S)AE Reporting”)
- Changes in vital signs, ECG, physical examination and laboratory test results, if they are judged clinically relevant by the Investigator.

If such abnormalities already pre-exist prior trial inclusion they will be considered as baseline conditions.

All (S)AEs, including those persisting after individual patient’s end of trial must be followed up until they have resolved, have been sufficiently characterized, or no further information can be obtained.

Pregnancy

In rare cases pregnancy may occur in a clinical trial. Once a patient has been enrolled into this clinical trial and has taken trial medication, the Investigator must report immediately (within 24 h) a potential drug exposure during pregnancy (DEDP) in a female patient or in a partner to a male patient to the sponsor’s unique entry point (country-specific contact details will be provided in the ISF). The Pregnancy Monitoring Form for Clinical Trials (Part A) should be used.

The outcome of the pregnancy associated with the drug exposure during pregnancy must be followed up and reported to the sponsor’s unique entry point on the Pregnancy Monitoring Form for Clinical Trials (Part B).

As pregnancy itself is not to be reported as an AE, in the absence of an accompanying SAE, only the Pregnancy Monitoring Form for Clinical Trials and not the SAE form is to be completed. If there is an SAE associated with the pregnancy then the SAE has to be reported on the SAE form in addition.

The ISF will contain the Pregnancy Monitoring Form for Clinical Trials (Part A and B).

Exemptions to (S)AE Reporting

Disease Progression has to be reported as SAE in the Phase I part. However, disease progression is an endpoint for analysis of efficacy in the Phase II part of the trial and as such is exempted from reporting as an (S)AE. Progression of the patient’s underlying malignancy will be recorded on the appropriate pages of the eCRF as part of efficacy data collection only and will not be reported on the SAE Form. It will therefore not be entered in the safety database (Adverse Reactions Information System global, ARISg) and hence not get expeditiously reported. Death due to disease progression is also to be recorded on the appropriate eCRF page and not on the SAE Form.

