6.2.1 Screening and run-in period

The screening period begins when the informed consent form is signed and ends just prior to the start of trial treatment on Day 1 of Cycle 1. The maximum duration of the screening period is 14 days and includes the randomization/treatment allocation.

Randomization/treatment allocation should be done as close as possible to the planned start of trial medication.

The following parameters and investigations will be obtained and/or performed:

- Informed consent (including mandatory biomarker assessments and mandatory pharmacogenetic testing)
- Informed consent for optional DNA-biobanking
- Demographics (sex, year of birth, race and ethnicity, smoking and alcohol status)

Proprietary confidential information © 2019 Boehringer Ingelheim International GmbH or one or more of its affiliated companies

- Medical history (oncological and relevant non-oncological) including detailed history of AML, previous malignant disease and previous therapies of malignant disease/other therapies
- WHO classification of the disease, date of first cytological diagnosis (month and year) and cytogenetics of AML
- Baseline conditions
- Review of inclusion and exclusion criteria (patient eligibility)
- Safety laboratory (hematology, biochemistry, coagulation, urine; for details please refer to [Section 5.3.6](#))
- Physical examination, height, weight, vital signs and ECOG performance score
- Serum pregnancy test in women of childbearing potential
- 12-lead ECG
- Bone marrow aspiration for disease assessment and biomarker. In case of *punctia sicca* disease assessment should be done via bone marrow biopsy.
- Molecular genetics and cytogenetics of AML (please refer to [Sections 5.5.1.1](#) and [5.5.1.2](#); available data from local analysis should be entered in eCRF; analysis at central laboratory will only be performed for patients in Phase II)
- Peripheral blood for disease assessment and biomarkers as per [Table 3](#)
- Documentation of adverse events (AEs) since signing the Informed Consent Form.
- Documentation of concomitant medications (including transfusions and anti-infectives) at trial entry and / or during screening
- Documentation of planned hospitalisations (only in source documents, not recorded in eCRF)
- Phase I Dose Escalation and Extension: Dose assignment via IRT (before the first administration of the trial drug and after informed consent and review of in- and exclusion criteria)
- Phase II: Randomization via IRT

Re-Screening

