5.2.2 Secondary endpoint(s)

Phase I

- Number of subjects with objective response combining
 - Complete remission (CR)
 - CR with incomplete blood count recovery (CRI)

- Time frame: From start of treatment until the earliest of progression, death or end of trial (approximately up to 30 months).

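### Marrow progression is measured from the blast count at AML diagnosis but partial remission from the pre-treatment marrow, so a relapsed or refractory patient with falling blasts can meet progression as written

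*Protocol*

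**What the plan says.** Protocol 5.2.1 uses two reference marrows in one response list.

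- **Partial remission** requires, among other things, a "decrease of pre-treatment bone marrow (baseline) blast percentage by at least 50" percent.
- **Progressive disease by marrow** is a "50% increase in BM blast count over baseline (AML diagnosis").
- **Progressive disease by blood** is a "50% increase in peripheral blast count over baseline that is considered clinically relevant by the Investigator". It carries no reference to diagnosis and adds a filter of clinical relevance that the marrow criterion lacks.

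Any one progression criterion is enough, and stable disease is what remains when remission and progression are both absent.

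Protocol 3.3.2 admits to Dose Escalation patients with "relapsed or refractory AML (defined as persisting AML after at least two induction cycles"). Extension patients are to be previously untreated. Screening (6.2.1) requires "Bone marrow aspiration for disease assessment and biomarker". For the first diagnosis it names the date, WHO class and cytogenetics, but no blast count.

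SAP 6.7 sets a default baseline, the last assessment before the first dose, which gives way where something else is specified. Deviation E1 in SAP Table 6.2:1 expects the baseline marrow within 14 days before first treatment.

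Progression has three consequences in Phase I:

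- The footnote to Protocol Table 4.1.3.1: 1 states "Only non-PD patients (i.e. patients without disease progression or relapse) will continue treatment within the trial".
- Protocol 5.3.9 states "Disease Progression has to be reported as SAE in the Phase I part".
- The response window in SAP 5.2.2 runs "From start of treatment until the earliest of progression, death or end of trial".

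**The concern.** A progression criterion should measure change on treatment. For a relapsed or refractory patient, the marrow at diagnosis may be separated from trial entry by induction courses or a remission, so comparing with it mixes the earlier disease course with the trial's effect. Two errors follow. A patient whose blasts are falling can be recorded as progressing, and a patient whose blasts are rising steeply can miss the marrow criterion.

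The first error matters more. Protocol Table 4.1.3.1: 1 plans further ten-day decitabine in Cycles 2 and 3 for patients whose marrow blasts are still 5% or more. A literal progression call would end treatment that the protocol means to give. The loss is hard to recover. The end-of-treatment marrow is largely waived when treatment ended for progression (6.2.2.1), and Phase I follow-up collects progression, relapse and death but not later remission (6.2.3.1.1).

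**Working it through.** There is no figure in the plan to reproduce; the check applies the definitions. Let D, S and T be the marrow blast percentages at diagnosis, at screening and on treatment. All blast values below are assumptions, because the documents give none.

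**Rules**

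- Marrow progression as written: T ≥ 1.5 × D
- Marrow progression on the pre-treatment reference: T ≥ 1.5 × S
- Falling blasts: T < S

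**Examples**

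| D / S / T (%) | T/D − 1 | T/S − 1 | As written | Pre-treatment reference |
|---|---|---|---|---|
| 20 / 60 / 35 | +75.0% | −41.7% | met (35 ≥ 30) | not met |
| 30 / 80 / 50 | +66.7% | −37.5% | met (50 ≥ 45) | not met |
| 40 / 90 / 65 | +62.5% | −27.8% | met (65 ≥ 60) | not met |
| 80 / 20 / 60 | −25.0% | +200% | not met (60 < 120) | met (60 ≥ 30) |

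The first patient was already 60/20 − 1 = +200% above diagnosis at screening, so the criterion was satisfied before any trial drug was given.

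**When falling blasts count as progression.** The condition is S > T ≥ 1.5 × D, which requires S > 1.5 × D. To avoid progression as written, the marrow must fall from screening by more than 1 − 1.5 × D/S. At S = 60%:

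- D = 20%: 1 − 30/60 = 50%, so T must be below 30%.
- D = 30%: 1 − 45/60 = 25%, so T must be below 45%.
- D = 40%: 1 − 60/60 = 0, so any fall is enough.

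On the pre-treatment reference, T < S can never meet the marrow criterion.

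**Opposite direction.** With D = 60% and S = 20%, the criterion is met from 1.5 × 60 = 90% as written and from 1.5 × 20 = 30% on the pre-treatment reference. If D exceeds 100/1.5 = 66.7%, the marrow criterion can never be met. The blood, extramedullary and investigator-judgement routes stay open.

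**Which categories conflict.** The partial-remission range ends at 25%, so its blast condition overlaps with marrow progression only if D ≤ 25/1.5 = 16.7%. The usual conflict is stable disease against progression.

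**Other reading of the 50%.** If it means percentage points, the problem remains: for 20 / 90 / 75 the rise from diagnosis is 55 points while the marrow falls from 90% to 75%.

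**The case against.** The strongest reply is that the parenthesis is a loose label for the trial-entry marrow. Both criteria use the word baseline, screening collects a marrow but names no diagnostic blast count, and deviation E1 treats the marrow just before treatment as the baseline. The gloss might also have been written once, at the first use of the word in the progression list. This reading is possible, but nothing in the documents states it, and partial remission a few lines earlier is worded explicitly as pre-treatment. If that was the intent, the fix merely records it.

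On the SAP, the default in 6.7 could be said to settle the matter, and parts of the SAP are redacted, so a progression derivation may sit there. The statement here is therefore limited: the wording of 6.7 does not by itself override a different reference given in the protocol.

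On consequences, Protocol 3.3.4.1 ties stopping to progression that creates an indication for other AML therapy, so a patient falling from 60% to 35% is not clearly forced off treatment by that section. The synopsis, Section 3.1, Flow Chart footnote 12 and the footnote to Table 4.1.3.1: 1 are stricter and end treatment at progression, so the consequence stands.

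Two further points are accepted. Few patients can be affected. Recruitment has ended, so changing the protocol cannot undo progression already recorded.

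**Conclusion.** The concern holds and is minor. As written, a relapsed or refractory patient with S > T ≥ 1.5 × D meets marrow progression while blasts fall. This rests on reading the parenthesis literally, which the text supports but which may not have been the intent; confidence is medium.

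The effect is confined to recorded progression and what follows from it. It concerns at most an unstated share of the 16 Dose Escalation patients, and among them only those whose screening blasts exceed 1.5 times the diagnostic value and whose on-treatment value lies between that multiple and the screening value. Previously untreated patients should have similar marrows at both times. CR and CRi require blasts below 5% and are not mislabelled. SAP 7.5 only lists response, with aggregated tables optional. Whether any patient was in fact misclassified cannot be told from the documents.

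**What to change.** In Protocol 5.2.1, replace the diagnosis reference in the marrow progression criterion with the pre-treatment marrow wording that partial remission already uses.

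In the SAP, add one sentence stating that marrow progression is derived on the 6.7 baseline. Show the derived status beside the recorded one. List every patient whose marrow progression status changes, and any CR or CRi recorded after such a progression. Leave progression by the other three criteria as recorded, and note that re-derivation cannot recover treatment or assessments already stopped.

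The cost is one phrase, one sentence and one listing. The screening marrow is already a required assessment. With recruitment closed, the SAP part carries most of the remaining value.

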5.3 ASSESSMENT OF SAFETY

After completion of recruitment to Phase I Extension Cohort A and Cohort B, the recruitment to this trial is discontinued.

With the aim to minimize the burden for trial participants, after approval of Protocol version 7.0, the mandatory protocol procedures described below in sections 5.3.4 (Physical Examination), 5.3.6 (Safety laboratory parameters), 5.3.7 (Electrocardiogram), are reduced for all patients who continue to receive trial medication in treatment cycles >7 . Instead, safety assessments should be performed at the investigator's discretion, based on standard medical care. For details refer to Flow Chart.

Findings are documented in the eCRF only if qualifying for an adverse event (see sections 5.3.8 and 5.3.9, unchanged).

5.3.1 Dose limiting toxicity (DLT)

DLT is defined as any non-disease-related non-hematological AE of CTCAE grade 3 or higher.

Expected non-hematological disease-related AEs will not be regarded as a DLT. These include complications resulting from hematological AEs such as:

- Bleeding and complications from bleeding due to thrombocytopenia as defined by the Investigator
- Infection and complications from infections due to neutropenia as defined by the Investigator
- Constitutional symptoms due to anaemia as defined by the Investigator

Infusion-related reactions (IRR) associated with the administration of BI 836858 should be reported as Adverse Event of Special Interest (AESI, refer to [Section 5.3.8.1](#)), but will not be regarded as a DLT. The exception is anaphylaxis which occurs despite premedication with glucocorticoid or which does not resolve with glucocorticoid (i.e. such cases of anaphylaxis will be regarded as a DLT).

Patients who do not receive at least 3 administrations of BI 836858 due to BI 836858-related toxicity are considered to have developed a DLT. If Cycle 2 is not started until 57th day from Day 1 of Cycle 1 as a result of drug-related AE, this AE is considered as DLT (i.e. treatment delay of \geq 4 weeks of the start of Cycle 2 due to drug-related AE). Patients who do not experience a DLT but do not receive all 3 planned administrations of BI 836858 during Cycle 1 for reasons other than toxicity or tolerability will not be evaluable for DLT and cannot be used to establish the MTD.

Infection will not constitute a DLT unless it is felt that the infection resulted from unexpectedly complicated myelosuppression; degree of severity and/or duration as assessed by the Investigator.

Since patients with refractory leukemia have infections and bleeding complications from myelosuppression, these events will not be considered as DLT unless they occur in the setting of prolonged myelosuppression from the combination treatment. Prolonged myelosuppression is defined as ANC < 1000/ μ L and PLT < 100,000/ μ L by day 56 of Cycle 1 in the setting of bone marrow showing < 5% blasts, without evidence of persistent cytogenetic abnormalities or minimal residual disease by flow cytometry. In case persistent cytogenetic abnormalities or immunophenotypic evidence of leukemia is present, myelosuppression would be considered secondary to leukemia even if morphology shows < 5% blasts.

All DLTs, occurring during the first or repeated treatment cycle will be reported as Adverse Event of Special Interest (AESI, see [Sections 5.3.8.1](#) for definitions and [5.3.9](#) for reporting requirements).

5.3.2 Maximum Tolerated Dose (MTD)

The MTD estimate after the dose escalation part of the trial will be obtained on the basis of DLTs observed during the first treatment cycle. However, for those patients who receive more than one cycle of the combination treatment, all AEs that constitute a DLT will be considered for re-estimation of the MTD based on the BLRM. To obtain this, the model will be re-run including the DLT information from all cycles. Based on both MTD estimates, the recommended dose for the extension cohort, the Phase II part and/or further development will be selected. In regular intervals, all available safety data including adverse events qualifying for DLT will be submitted to the SMC. The SMC will assess this information and provide recommendations for trial conduct and dose escalation.

The SMC may recommend stopping the dose finding part of the trial after the criterion for MTD is fulfilled (refer to [Section 7.1](#)). Further patients may be included to confirm the MTD. If no DLT is observed at a dose of which the efficacy is considered sufficient, the SMC may

decide to include additional number of patients at this dose level and to declare this dose as the RExP1D (Recommended Extension Phase I Dose), that will be used for the Phase I Extension part of the trial.

